Background and Rationale	
DSL^P have developed a topical cream containing rapamycin 0.5% and 1.0% referred to as Rapamycin cream, topical.
 
Tuberous Sclerosis Complex (TSC) is a disorder characterized by the development of multiorgan benign tumor-like growths in any part of the body. TSC is caused by mutations in the TSC1 and TSC2 genes which encode a growth suppressor complex that inhibits the mTOR (mammalian Target Of Rapamycin) protein. Loss of regulation of mTOR leads to abnormal differentiation and development, and to the generation of enlarged cells.
 
Facial angiofibromas (FA) are present in 70-80% of patients with TSC and are commonly developed after the first two years of life. FA are distinguished as fibrous and/or highly vascular papules. Facial angiofibromas in patients with TSC are thought to develop due to the mutational activation of the mTOR pathway.
 
These growths tend to spontaneously bleed or can be affected by slight traumas that can also cause uncontrolled bleeding. When present around the eyes, nose and mouth infections become common. Due to their progressive nature, FA can impair vision and breathing.
 
Rapamycin, a macrocyclic antibiotic produced by Streptomyces hygroscopicus, is a potent inhibitor of mTOR. Although the mechanism of action of rapamycin is not completely understood, research has shown that when rapamycin binds to mTOR, the activity produced by the mTOR cascade pathway is inhibited, thus restraining uncontrolled cellular proliferation.
 
A number of clinical studies have used different concentrations (0.003-1%) of topical rapamycin for the treatment of FA associated with TSC. Taken as a whole, these studies demonstrate the potent efficacy and great tolerability of topical rapamycin for FA. All cases reported reduction of erythema, papule size and lesion flattening, and improved skin texture.
 
The efficacy and safety of two rapamycin strengths (0.5% and 1.0%) will be assessed during a 26 week double-blind treatment phase with assessments made at clinical visits at baseline, 2, 8, 14, 20 and 26 weeks, and at follow-up (4 weeks after the last dose of study drug).

Study Hypothesis	It is hypothesized that the two strengths of Rapamycin cream, topical will improve the appearance of FA associated with TSC compared to placebo. It is also expected that both strengths will be well tolerated.
Study Design	A Phase 2/3, multi-center, double-blind, placebo-controlled, randomized, parallel-group, dose-response study
Duration of Treatment	26 weeks
Test Product, Dose, Mode of Administration	
Rapamycin formulated as a topical cream (Rapamycin cream, topical) of different dose strengths: 0.5% and 1.0%.
 
Rapamycin cream, topical will be applied once daily for 26 weeks on the surface of the facial angiofibroma lesions. The amount of cream required to produce a thin confluent layer on the skin is 6 mg/cm². The amount to be applied will be based on the size of the affected area.

Reference Product, Dose, Mode of Administration	A placebo cream will be applied daily for 26 weeks on the surface of the facial angiofibroma lesions.
Number of Participants	
40 per treatment group
 
It is anticipated that no more than 10% of the placebo group will achieve the primary endpoint, a successful treatment according to IGA scale after 26 weeks treatment and that each dose of Rapamycin cream, topical will achieve at least 40% successful treatment. Including the Holm-Bonferroni adjustment of the type I error rate for multiple comparisons ($\alpha = 0.025$) a sample size of 40 participants per group is required in each randomized group to achieve >80% power for these comparisons.

Criteria for Inclusion	
Inclusion Criteria
 
 1. Male and female patients aged ≥ 6 years and ≤ 65 years on the day informed consent is obtained 2. Patients diagnosed with TSC based on the clinical diagnostic criteria of International Tuberos Sclerosis Complex Consensus Conference 2012 and presenting visible facial angiofibroma 3. An FA severity score of 2 or 3 on the IGA scale 4. Patients or their legal representatives capable of understanding the explanation of the clinical trial and who give written informed consent for participation 5. Patients or their legal representatives able to maintain patient diaries following the instructions of the investigator or sub-investigator 
Exclusion Criteria
 
 1. Patients who cannot carry out the treatment plan or follow-up assessment 2. Patients with serious skin lesions such as erosions or ulcers 3. Patients with known hypersensitivity to any component of the study product 4. Patients who have received rapamycin/sirolimus, everolimus, or temsirolimus within 3 months of enrolment 5. Patients who received laser therapy or surgical therapy within 6 months prior to trial enrolment 6. Patients who participated in any other clinical trial within 3 months prior to the day of enrolment 7. Patients judged unsuitable for this clinical trial by the investigator or sub-investigator 8. Pregnant or lactating females 9. Sexually active females of childbearing potential not using adequate contraception and sexually active males not using adequate contraception 10. Patients with immune dysfunction or receiving any form of immunosuppression 11. Patients with severe FA, with a score of 4 on the IGA scale 12. Patients with an FA severity score of less than 2 on the IGA scale 						
Brief Description	
The study can be divided into a Screening Phase, a Treatment Phase and Follow-up.
 
The Screening Phase includes collection of Informed Consent and the assessment of the subjects' suitability for the study. Eligible subjects will be assigned a unique randomization number before the first application of the study drug. Subjects will be randomized to receive treatment with one of two strengths of Rapamycin cream, topical (0.5% and 1.0% rapamycin, respectively) or placebo.
 
The Treatment Phase of the study comprises one clinical visit at baseline (V0) and 5 subsequent clinical visits after 2, 8, 14, 20 and 26 weeks treatment (V1-5) with Rapamycin cream, topical or placebo. The amount of cream will be based on the total area of the facial lesion(s) and patients will be instructed to apply the formulation every evening, about half an hour before retiring for bed, for 26 weeks.
 
Follow-up will be performed 28 days after the V5 visit, or the last visit where early withdrawal from treatment was confirmed.
 
Assessment of the extent and severity of facial angiofibroma will be performed at randomization, at each clinical visit (V1-5) and at follow-up using a variety of measures including an Investigator's Global Assessment (IGA) scale, the facial angiofibroma severity index (FASI), as well as subjective and objective improvement ratings.
 
The primary efficacy endpoint is based on the IGA scale, described below:
 
  
 Grade	Short Description	Detailed Description	
   
 0	Clear	No signs of facial angiofibroma	
  
	Grade	Short Description	Detailed Description	0	Clear	No signs of facial angiofibroma
Grade	Short Description	Detailed Description					
0	Clear	No signs of facial angiofibroma					

1	Almost Clear	Few small angiofibromas (< 2 mm); normal to pink coloration in affected area*
2	Mild	Predominantly small angiofibromas (< 2 mm) with few intermediate tumors (2-4 mm); pink to red coloration in affected area
3	Moderate	Predominantly intermediate angiofibromas (2-4 mm) with few large tumors (> 4 mm); red coloration in affected area
4	Severe	Mix of intermediate (2-4 mm) and large angiofibromas (>4 mm) present diffusely on face; intense and generalized redness on the whole face

* Note: coloration refers to both the FA lesions and the background facial skin tone
Where lesion size and coloration are discrepant within the grade, emphasis should be placed on lesion size.

The following medications are prohibited after enrolment in this trial due to the risk of interference in the evaluation of efficacy/safety:

- Laser and surgical treatment of the target treatment area
- Administration of mTOR inhibitors (rapamycin/sirolimus, everolimus, temsirolimus etc.)
- Application of steroidal or antibacterial agents to the target area
- Administration of cyclosporine or macrolide antibiotics
- Strong inhibitors of CYP3A4 and/or P-gp (such as ketoconazole, voriconazole, itraconazole, erythromycin, telithromycin, or clarithromycin) or strong inducers of CYP3A4 and/or P-gp (such as rifampin or rifabutin)

Evaluation of Efficacy	
Primary Endpoint: The percentage of patients obtaining successful treatment based on a blind assessment using the IGA scale after 26 weeks treatment or at last visit if early withdrawal/discontinuation
 
Secondary Endpoints:
 
 • Time to treatment success • Change from baseline in IGA after 26 weeks treatment or at last visit if early withdrawal/discontinuation • Change from baseline in FASI after 26 weeks treatment or at last visit if early withdrawal/discontinuation • Subjective (patient or parent/caregiver) improvement rating from first visit (V0) after 26 weeks treatment or at last visit if early withdrawal/discontinuation • Objective (clinician) improvement rating from first visit (V0) after 26 weeks treatment or at last visit if early withdrawal/discontinuation • Categorical Improvement of Facial Angiofibroma from first visit (V0) after 26 weeks treatment 
Exploratory Endpoints:
 
 • The percentage of patients with successful treatment according to IGA scale after 2, 8, 14 and 20 weeks treatment • Change from baseline in IGA after 2, 8, 14 and 20 weeks treatment • Change from baseline in FASI after 2, 8, 14 and 20 weeks treatment • Change from baseline in each FASI component (erythema, size, extension) after 2, 8, 14, 20 and 26 weeks treatment • Subjective (patient or parent/caregiver) improvement rating from first visit (V0) after 2, 8, 14 and 20 weeks treatment • Objective (clinician) improvement rating from first visit (V0) after 2, 8, 14 and 20 weeks treatment • Change in IGA from week 26 to Follow up (4 weeks after final dose) • Change in FASI from week 26 to Follow up (4 weeks after final dose)
Evaluation of Safety	
Safety will be assessed at each of the visits and will include:
 
 • the local and systemic tolerability of different doses of topical rapamycin (i.e. reporting of adverse events), including, known topical and known oral rapamycin adverse events. • A physical examination, measurement of vital signs, and tests of hematology, biochemistry, blood lipids and urinalysis at baseline, at each visit (V1-5), and at follow-up • Rapamycin blood concentration, performed at baseline, at each visit (V1-5), and at follow-up
Statistical Methods	
The Intent-To-Treat (ITT) population will consist of all subjects who receive at least one dose of study drug. Subjects will be included in the group to which they were randomized irrespective of the treatment actually taken. The ITT population is the primary population for the efficacy analysis. The safety population will include all subjects who are treated with study drug, with group determined by the actual dose of study drug taken.
 
Primary Endpoint: The data for the primary endpoint, the percentage of patients obtaining successful treatment after 26 weeks, or at last visit if early withdrawal/discontinuation, based on

	
the blind assessment using the IGA scale, will be summarized by treatment group. Success is defined as clear or almost clear with an improvement of at least two grades from baseline, i.e. 2 to 0; 3 to 1. Statistical analysis of the primary endpoint will be performed using a logistic regression model which will include treatment effect and stratum as fixed factors and baseline IGA score as a covariate. This model will be used to generate the odds ratios and 95% confidence intervals of the individual dose treatments compared with placebo, with the p-values for these comparisons adjusted using the Holm-Bonferroni adjustment.
 
Secondary Endpoints: The time-to-treatment success will be summarized using Kaplan-Meier analyses and compared between each dose group and placebo using the stratified log-rank test. The secondary endpoints change in IGA and FASI from baseline to 26 weeks/last assessment, and objective and subject improvement from baseline to 26 weeks/last assessment, will be summarized by treatment group using means, medians, standard deviations, interquartile ranges and minima and maxima. These changes will be analyzed using ANOVA including treatment and stratum as main effect fixed factors, with planned pairwise comparisons between each dose group and placebo. If the data is not adequately normally distributed the Kruskal-Wallis non-parametric ANOVA, and Mann-Whitney U tests comparing changes between treatment groups will be used for the analysis. Baseline for the IGA and FASI scores is defined as the last pre-treatment assessment, whether obtained at screening, randomization or V0.
 
Categorical Improvement scores will be compared amongst study groups using the Kruskal-Wallis non-parametric ANOVA, and Mann-Whitney U tests comparing changes between each dose group and placebo.
 
The type I error rate associated with the testing of the six secondary endpoints will be strictly controlled using the Hochberg procedure. This will involve ranking the 6 p-values derived from the testing of each dose group with placebo from highest to lowest. If the highest p-value is <0.05, then all six comparisons are considered statistically significant. If not significant then the next highest is tested at p=0.025. The p-value continues to reduce at each non-significant step based on the Bonferroni adjustment.
 
Exploratory Endpoints: The exploratory endpoints, including the change in IGA and FASI from week 26 to follow-up, will be analyzed in the same manner as the appropriate secondary endpoints. The p-values for these comparisons will not be reported but the differences between each dose group and placebo will be summarized as odds ratios or mean differences as appropriate with 95% confidence intervals.
 
Safety Endpoints: Safety Endpoints: AEs will be collected for all randomized participants and will be listed with type of AE, severity and relationship for each treatment group, using the safety population. Adverse event data will be summarized for each treatment groups using frequencies and percentages (% of participants with each specific AE). If frequencies permit, Chi-square tests or fisher's exact tests may be used to compare the rates of occurrence between treatment groups. Known AEs specific to oral or topical rapamycin will be individually summarized by treatment group.
 
Between-treatment comparisons will be made for changes in vital signs, hematology, biochemistry, blood lipids and urinalysis from baseline at visits V1-5. Baseline is defined as the last pre-treatment assessment, whether obtained at screening, randomization or V0. Changes between V5 and Follow-up will also be examined.
 
Blood rapamycin concentrations will be summarized for each of the treatment groups at all scheduled timepoints using standard descriptive statistics (means, medians, geometric means, ranges, standard deviations and standard errors), as appropriate.
 
Adverse events will be monitored up to 4 weeks after administration of the final dose of study medication.

--	---

Schedule of assessments	Assessment	Screening Phase			Treatment Phase						Follow-Up
		Informed consent	Screening	Randomization	V0 Baseline	V1 2 weeks	V2 8 weeks	V3 14 weeks	V4 20 weeks	V5 26 weeks	4 weeks after final dose
	Tolerance	≤3 months before V0	≤14 days before V0		NA	±3 days	±3 days	±3 days	±3 days	±3 days	±5 days
	Informed consent	X ¹									
	Inclusion/exclusion criteria		X								
	Demographic data		X								
	Medical history		X								
	Physical examination		X			X	X	X	X	X	X
	Vital signs		X	X	X	X	X	X	X	X	X
	Pregnancy test ²		X		X	X	X	X	X	X	
	Hematology, biochemistry & lipid panel ³		X			X	X	X	X	X	X
	Urinalysis		X			X	X	X	X	X	X
	Blood rapamycin concentration ^{3,4}		X			X	X	X	X	X	X
	Drug administration (once daily, evenings)				X						
	Photographs of FA			X		X	X	X	X	X	X
	IGA		X	X		X	X	X	X	X	X
	FASI			X		X	X	X	X	X	X
	Percentage improvement (subjective & objective)					X	X	X	X	X	
	Categorical improvement									X ⁵	
	Concomitant medications		X	X	X						X
	Adverse events				X						X

¹ if more than a month passes between obtaining informed consent and randomization, then informed consent should be re-obtained

² only conducted for women of childbearing potential

³ if participants are unable to provide blood samples at all timepoints, the minimum to be collected should be samples at screening, V1 or V2 and V5

⁴ blood sampling collected prior to the daily evening dose

⁵ categorical assessment only to be done at V5, unless early withdrawal/discontinuation, in which case categorical assessment should be completed at last visit

TABLE OF CONTENTS

Protocol Synopsis	6
Table of Contents	14
List of Figures.....	16
List of Tables	16
List of Abbreviations	17
1. Introduction.....	18
1.1 Background	18
1.2 Study Drug Rationale	19
1.3 Study Rationale	22
1.4 Known and Potential Risks and Benefits.....	22
2 Trial Objectives	23
2.1 Hypothesis	23
2.2 Efficacy Objectives	23
2.3 Safety Objective	24
3 Investigational Plan.....	24
4 Participant population	26
4.1 Number of Participants.....	26
4.2 Inclusion Criteria	26
4.3 Exclusion Criteria	26
4.4 Withdrawal Criteria	27
4.5 Study or Study Site Termination and Subject Discontinuation.....	27
4.5.1 Study or Study Site Discontinuation.....	27
4.5.2 Subject Discontinuation.....	27
5 Treatments.....	28
5.1 Treatments to be administered	28
5.1.1 Treatment Phase	29
5.2 Investigational Products	29
5.3 Randomization.....	29
5.4 Blinding	30
5.5 Prohibited concomitant medications	30
5.6 Treatment compliance.....	31

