Although a range of concentrations appear to be effective, adults tended to have a poorer response to treatment than children for a given strength, suggesting the need for higher concentrations in this age group where FA are typically more severe (33,45,46). There is some data to suggest that higher concentrations have greater efficacy, particularly in adult patients (37,45). Moreover, most authors suggested the use of topical rapamycin at early stages (in younger patients) so optimal results can be achieved.

Table 1: Published Clinical Trials for Topical Rapamycin for Facial Angiofibroma

Study	Study Design	Strength	N	Frequency and Duration of therapy	Efficacy
Wataya-Kaneda et al., 2018	Multicenter, double-blind, randomized, placebo-controlled, parallel group	0.2%	62	2x daily for 12 weeks	
Primary endpoint: composite improvement in angiofibromas (size and color at 12 weeks). Response rate of angiofibromas at weeks 4, 8, and 12 of treatment was 0 in the placebo group in contrast to 20%, 43% and 60% in the rapamycin group. None of the 31 assessable patients in placebo group were rated improved or better and 26 of them were rated unchanged. In contrast 17% and 43% patients in the rapamycin group were rated “markedly improved” and “improved”, respectively.
 
In the rapamycin group the response rates were significantly higher in the pediatric patients (85%) than in adult patients (41%) at week 12 (p=0.03)
 
Rapamycin gel, 0.2% demonstrated a significant clinical benefit for patients with TSC involving angiofibromas, thus providing a promising therapeutic modality.

Koenig et al., 2018	Multicenter, double-blind, randomized, vehicle-controlled, parallel group	0.1% 1%	179	1x daily at bed time for 6 months	
Clinically meaningful and statistically significant improvement in facial angiofibroma was observed for both 1% and 0.1%. At 6 months, Angiofibroma Grading Scale (AGS) mean improvement for 1% was 16.7 points compared with 11.0 for 0.1% and 2.1 points for vehicle only (P<0.001 for 1% and 0.1% vs vehicle only). End-of-treatment photos were rated “better” for 81.8% of patients in the 1% rapamycin group, compared with 65.5% for those in the 0.1% rapamycin group and 25.5% for those in the vehicle-only group (P<0.001, all 3 pairwise comparisons).
 
Topical rapamycin was generally well-tolerated with no measurable systemic absorption.

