10.3.2 Secondary Efficacy Endpoints

The time-to-treatment success will be summarized using Kaplan-Meier analyses and compared between each dose group and placebo using the stratified log-rank test. The secondary endpoints change in IGA and FASI from baseline to 26 weeks/last assessment, and objective and subject improvement from baseline to 26 weeks/last assessment, will be summarized by treatment group using means, medians, standard deviations, interquartile ranges and minima and maxima. These changes will be analyzed using ANOVA including treatment and stratum as main effect fixed factors, with planned pairwise comparisons between each dose group and placebo. If the data is not adequately normally distributed the Kruskal-Wallis non-parametric ANOVA, and Mann-Whitney U tests comparing changes between treatment groups will be used for the analysis. Baseline for the IGA and FASI scores is defined as the last pre-treatment assessment, whether obtained at screening, randomization or V0.

Categorical Improvement scores will be compared amongst study groups using the Kruskal-Wallis non-parametric ANOVA, and Mann-Whitney U tests comparing changes between each dose group and placebo.

The type I error rate associated with the testing of the six secondary endpoints will be strictly controlled using the Hochberg procedure. This will involve ranking the 6 p-values derived from the testing of each dose group with placebo from highest to lowest. If the highest p-value is <0.05 , then all six comparisons are considered statistically significant if not significant then the next highest is tested at $p=0.025$. The p-value continues to reduce at each non-significant step based on the Bonferroni adjustment.

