10.3.4 Additional Analyses

A sensitivity analysis will be conducted using the Per-Protocol (PP) population to assess the robustness of the results for the primary endpoint.

An additional sensitivity analysis of the primary endpoint will be conducted in the portion of the ITT who complete the 26 week treatment period and have a 26 week assessment, if this population differs from the PP population.

A further sensitivity analysis will be conducted in which those patients who do not provide data at 26 weeks will be considered as treatment failures.

Analyses and summaries of the primary endpoint will also be presented by subgroup. These will include gender, age, site and baseline IGA score groups. As the sample sizes of subgroups are likely to be small,

these analyses will be presented for information purposes only, and statistically significant results are not anticipated.

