10.5 Missing data

Every effort will be made to obtain all assessments at the appropriate time points from all randomized participants, especially to obtain assessments from early withdrawals. Where early withdrawals occur between visits without a visit to confirm subject withdrawal, assessments completed at the visit preceding withdrawal will be considered the assessment at discontinuation/withdrawal.

For the exploratory analyses, intermittent missing values in the analysis of IGA, FASI and percentage improvement scores will be imputed by linear interpolation of adjacent scores (i.e. immediately preceding and immediately following the missing value). No attempt will be made to impute missing data for Overall Improvement/Patient Satisfaction (recorded only at V5, or at last visit where withdrawal was confirmed).

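### Change in IGA and FASI at week 26 uses a withdrawn patient's last score, so these secondary comparisons carry a bias whose size and direction the plan has little means of showing

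*Combined protocol and SAP*

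**What the plan says.** The synopsis and sections 2.2 and 6.1.2 define secondary endpoint 2 as "Change from baseline in IGA after 26 weeks treatment or at last visit if early withdrawal/discontinuation" and endpoint 3 as "Change from baseline in FASI after 26 weeks treatment or at last visit if early withdrawal/discontinuation". Section 10.5 asks for every effort to assess early withdrawals. If a patient leaves between visits and no withdrawal visit takes place, "assessments completed at the visit preceding withdrawal will be considered the assessment at discontinuation/withdrawal". That earlier visit can be V1, at week 2.

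Section 10.3.2 treats "change in IGA and FASI from baseline to 26 weeks/last assessment" as a single value per patient: "These changes will be analyzed using ANOVA including treatment and stratum as main effect fixed factors". Rank tests replace the ANOVA if the data are not adequately normal. Both scales are scored at all five visits (Table 3, section 7.2.2), but weeks 2 to 20 feed only exploratory endpoints.

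Section 10.3.4 lists three missing-data sensitivity analyses: per-protocol, completers, and the one described as "A further sensitivity analysis will be conducted in which those patients who do not provide data at 26 weeks will be considered as treatment failures". All three concern success on the primary endpoint.

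**The concern.** This is last observation carried forward, and the carried value enters the analysis as if it had been observed at week 26. Scores taken weeks apart need not be interchangeable. In Table 1, the 62-patient trial of a 0.2% gel reports: "Response rate of angiofibromas at weeks 4, 8, and 12 of treatment was 0 in the placebo group in contrast to 20%, 43% and 60" per cent on active. If the effect builds in that way, an early carried score costs the active arms more than placebo. If benefit fades once treatment stops, as section 1.2 says some data show, a carried on-treatment score flatters the active arms instead.

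These endpoints are meant to support claims, since section 10.3.2 promises strict type I error control for them. Section 10.6 also allows missing-data procedures to change in response to results, so the choice is best fixed beforehand.

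**Working it through.** **The plan's own figure.** The plan gives no mean, SD, power or dropout rate for change in IGA or FASI. Its one design figure is for the primary endpoint: 10% against 40%, alpha 0.025 (taken as two-sided), 40 per group, more than 80% power. Without continuity correction, n = [2.241 × √(2 × 0.25 × 0.75) + 0.842 × √(0.09 + 0.24)]² / 0.30² = 38.3, so 39 per group, with 82.0% power at 40. The figure reproduces but says nothing about these secondaries or about dropout.

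**Inputs assumed.** Dropout d of 10% or 20% per arm, a flat placebo mean, and three curves for f, the share of the week-26 effect reached at V1 to V4:
- Linear to week 26: 2/26, 8/26, 14/26, 20/26 (mean 0.423).
- Plateau, from the 20/43/60% rates: 10/60 (half the week-4 rate), 43/60, 1, 1 (mean 0.721).
- Fast, half-time one week: 0.75, then about 1 (mean 0.937).

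**Target A, effect had patients stayed on treatment.** Share retained by carry-forward = (1 − d) + d × mean f. Linear curve, even spread of dropout over V1 to V4, d = 0.20: 0.80 + 0.20 × 0.423 = 0.885.

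**Target B, actual week-26 status with benefit fully lost after stopping.** The true effect is 1 − d, so the ratio is retained / (1 − d). Same case: 0.885 / 0.80 = 1.106.

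| Curve | d | A: even spread | A: all last seen week 2 | B: even spread | B: all last seen week 2 |
|---|---|---|---|---|---|
| Linear | 10% | 0.942 | 0.908 | 1.047 | 1.009 |
| Linear | 20% | 0.885 | 0.815 | 1.106 | 1.019 |
| Plateau | 10% | 0.972 | 0.917 | 1.080 | 1.019 |
| Plateau | 20% | 0.944 | 0.833 | 1.180 | 1.042 |
| Fast | 10% | 0.994 | 0.975 | 1.104 | 1.083 |
| Fast | 20% | 0.987 | 0.950 | 1.234 | 1.188 |

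Under A the understatement runs from 0.6% to 18.5%. Under B the overstatement runs from 1% to 23%.

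**Power under A.** Set the effect for 80% power with complete data at two-sided 0.05 (the first Hochberg step), 40 per arm, SD unchanged. Power is then Φ(retained × 2.80 − 1.96). On the linear and plateau curves with even spread it falls to 75–78% at 10% dropout and 70–75% at 20%. It falls to 63–65% at 20% if all leave after week 2.

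**Unequal dropout.** Assume FASI changes of −1.2 active and −0.4 placebo (true difference −0.80), with 10/50/75/90/100% of each reached at V1 to V5. Mean f is 0.5625 with even spread, and 0.30 if patients are last seen at V1 or V2.
- 10% in each arm: −0.80 × (0.90 + 0.10 × 0.5625) = −0.765; the early pattern gives −0.744. That is 4–7% low.
- 20% active, 10% placebo: −1.2 × 0.9125 + 0.4 × 0.95625 = −0.7125; early, −1.2 × 0.86 + 0.4 × 0.93 = −0.66. That is 11–18% low.
- 10% active, 20% placebo: −1.1475 + 0.365 = −0.7825; early, −1.116 + 0.344 = −0.772. That is 2–4% low.

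**Dropout for lack of effect.** In a simulation with effect 1.0, SD 1.5, visit correlation 0.6, 10% active and 30% placebo dropout, patients with worse scores were more likely to leave. Carry-forward gave 1.04 (linear) and 1.07 (plateau), against 1.00 with complete data. With the same rates but dropout unrelated to score it gave 0.93 and 0.98. The reason for leaving decides the direction.

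**The case against.** A reader might infer that carry-forward necessarily understates the drug effect. The documents do not support that. The rising response in Table 1 comes from one trial of another strength, given twice daily, with a responder endpoint ending at week 12. The same table has a ten-patient series with a 4-week median time to response and a four-patient series improving within 1 week. These are small and uncontrolled, but they point to the fast curve. The flat placebo arm is also not universal: in the 179-patient trial, 25.5% of vehicle patients had photographs rated better. Section 1.2's remark on loss of benefit points to overstatement of actual week-26 status.

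A reader might also infer that no planned analysis avoids carry-forward. Exploratory endpoint 4 gives each FASI component at week 26 with no last-visit clause, and section 10.5 imputes only intermittent gaps there. It is a partial view: it is exploratory and does not give the FASI total. Change in IGA has no counterpart; the section 10.3.4 analyses see IGA only as success or failure.

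It is fair to add that the preceding visit is a fallback, so a week-2 score is possible rather than typical. At 10% dropout per arm the FASI bias is only about 0.04 to 0.06 points in the example above. If the bias is towards understatement it is conservative for superiority. That limits the severity. It does not settle the matter, because the direction cannot be relied on.

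**Conclusion.** The point holds in a direction-neutral form. The last-visit rule mixes time points and targets neither of the two effects a reader would want. Under assumed dropout of 10 to 20%, the bias for an on-treatment target is about 1 to 18% towards understatement. It is largest when the effect builds slowly and patients leave early, and near 1% when onset is fast and dropout is spread evenly. It becomes an overstatement against actual week-26 status if benefit is lost, or if placebo patients leave for lack of effect. Every figure rests on assumed curves and dropout rates, since the documents supply neither. What the documents do settle is that V1 to V4 scores from patients who stay go unused in these comparisons, that no target effect is stated, and that the section 10.3.4 sensitivity analyses stop at the primary endpoint. Section 4.5.2 keeps patients in the study after dosing stops for an adverse event, yet nothing says whether their later scores count. The change is worth making for endpoints under type I error control; it does not touch the primary endpoint.

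**What to change.** In section 10.3.2 and the synopsis:
- State the target effect, and whether scores after stopping study drug count.
- Make the main analysis of change in FASI and change in IGA a repeated-measures model on observed V1 to V5 scores. Include treatment, visit, treatment-by-visit, stratum, baseline score and baseline-by-visit, with unstructured covariance. Take the week-26 dose-versus-placebo contrasts from it and test them under the plan's Hochberg procedure.
- Keep the last-visit ANOVA or rank test as a sensitivity analysis. The rank test matters most for the five-level IGA, where a normal model is only an approximation.
- Add one reference-based imputation analysis, in which patients who leave an active arm are assumed to behave like placebo afterwards.

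The cost is SAP wording and some programming; no new visits or data are needed. The model assumes that dropout is explained by observed scores, which is why the reference-based analysis is needed. Its standard error will be slightly larger than with carry-forward.
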